4.6 PRN1008 Inpatient Dose Adjustment

Part A: Initial PRN1008 dosing will be 400 mg *bid*, with inpatient dose adjustment based on clinical response and tolerability, supplemented by BTK occupancy ([Table 2](#)).

Part B: Initial PRN1008 dosing will be 400 mg qd, with intra-patient dose escalation to 400 mg *bid* allowed at or after Week 3 visit for insufficient clinical response (see [Table 3](#)) (and then again to 600 mg *bid* if necessary at or after Week 5 visit. Corticosteroid rescue treatment will be initiated, if indicated ([Appendix 1](#)).

“Well tolerated” is defined as the absence of Grade 3 or greater gastrointestinal AEs, or Grade 2 non-gastrointestinal AEs, including liver function changes, related to PRN1008 therapy. Investigators should use their judgment of the risk-benefit of continuing therapy by weighing the extent of clinical response, and AEs potentially related to PRN1008 therapy. In general, PRN1008 should be stopped and conventional therapy started when tolerability is poor and clinical response is also suboptimal.

Table 2 (Part A) General Dose Adjustment Guidelines for Dose Selection in the First 4 Weeks

Clinical Response	Trough BTK Occupancy	Tolerability*	Action
Responder 400 mg bid	≥ 50%	Well Tolerated	Maintain 400 mg bid Taper corticosteroids if used in combination
		Poorly Tolerated	Reduce to 300 mg bid Taper corticosteroids if used in combination
	< 50%	Well Tolerated	Maintain 400 mg bid Taper corticosteroids if used in combination
		Poorly Tolerated	Reduce to 300 mg bid Taper corticosteroids if used in combination
Suboptimal Response 400 mg bid	≥ 50%	Well Tolerated	Follow rescue criteria if triggered, if not maintain dose at 400 mg bid
		Poorly Tolerated	Follow rescue criteria if triggered, if not maintain dose at 400 mg bid if feasible
	< 50%	Well Tolerated	Follow rescue criteria if triggered, if not, increase dose to 600 mg bid
		Poorly Tolerated	Follow rescue criteria if triggered, if not, increase dose to 600 mg bid if tolerability allows.

* “Well tolerated” is defined as the absence of Grade 3 or greater gastrointestinal AEs, or Grade 2 non-gastrointestinal AEs, including liver function changes, related to PRN1008 therapy.

Table 3 (Part B) General Dose Escalation Guidelines

Current Dose	Inadequate Clinical Response* Dose-escalation Rules
400 mg qd	Increase to 400 mg bid (allowed at Week 3 visit or later)**
400 mg bid	Increase to 600 mg bid (allowed at Week 5 visit or later)**
600 mg bid	No dose increase possible. See Appendix 1B for corticosteroid rescue protocol

[figure not shown]
* Investigator discretion: Generally, clinical response is shown by some improvement seen in first 2 weeks with CDA achieved by the Week 5 visit

** Unless tolerability issues preclude dose-escalation

[figure not shown]

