1.3 Summary of PRN1008 Animal Toxicity Studies

1.3.1 13-week GLP Toxicology

In the 13-week repeat-dose GLP toxicity studies with PRN1008, doses of up to 500 mg/kg/day and 300 mg/kg/day were given to rats and dogs, respectively. The No Observed Adverse Effect Level (NOAEL) in rats was considered to be 150 mg/kg/day and the NOAEL for male dogs was 30 mg/kg/day. The NOAEL in female dogs is less than 30 mg/kg/day, based on body weight loss in one female administered 30 mg/kg/day. At doses above 150 mg/kg, the lungs of some rats showed increased macrophages and bronchoalveolar papillary hyperplasia. In dogs, PRN1008-related findings considered potentially PRN1008-related were observed in the liver and lymphoid tissues. At doses above 30 mg/kg in dogs, changes in liver function (mainly ALT and AST), loss of appetite, and associated weight loss were observed. These observations are considered clinically significant and their assessment in human subjects is included in the study procedures in this clinical protocol.

Orally administered PRN1008 did not affect the gross behavioral, physiological, or neurological state of rats at dose levels up to 500 mg/kg, and the NOAEL for effects on the cardiovascular and respiratory systems in dogs was considered to be 500 mg/kg.

PRN1008 tested negative in a battery of in vitro and in vivo genotoxicity studies.

1.3.2 6 and 9-month GLP Toxicology

In the 6-month rat oral GLP toxicology study, the no-observed-adverse-related level (NOAEL) was 50 mg/kg/day in females (AUC_{last} 5480 hr.ng/mL) and 150 mg/kg/day in males (AUC_{last} 5327 hr.ng/mL). The nature and severity of observed findings included lethality, decreased body weight gain, macroscopic and microscopic changes in the gastrointestinal tract, and neutrophilic inflammation in the brain. Adequate safety factors of ~4X are present to the rat NOAEL, assuming a maximum exposure in humans of 1360 ng.h/mL with a 600 mg bid dose, and 6X to the target exposure of 890 ng.h/mL with the 400 mg bid dose.

In the 9-month dog oral GLP toxicology study, the NOAEL for male and female animals was 30 mg/kg/day (AUC_{last} 963 hr.ng/mL), based on body weight loss that required food supplementation and the euthanasia of one male dog dosed at 50mg/kg/day. The observed findings in the dog of appetite decrease, weight loss, and reversible changes in liver function are readily monitorable in human studies.

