2 RATIONALE AND JUSTIFICATION FOR THE STUDY AND THE STUDY DESIGN

2.1 Rationale for the Study Design

This open-label, pilot study is designed to explore the initial efficacy and safety of PRN1008 in PV and to enable the accurate design of pivotal randomized clinical trials which are to follow. An open-label design was chosen for several reasons: PV does not spontaneously remit so there is no placebo effect to account for; clinicians need to know when to use rescue corticosteroids, if necessary, in a timely manner; and lastly, the pilot nature of the investigation itself is best explored in an open-label fashion.

Because of the ability to guide individualized dosing with BTK occupancy measurement, the use of which has been validated in a naturally occurring canine pemphigus study, this assay was used to supplement the clinical response assessments in making dose-adjustments in **Part A**. More than 95% of patients in **Part A** (20/21) had adequate BTK occupancies (mean 86% pre dose at steady-state). In **Part B**, the clinical efficacy of the 400 mg qd dose is being explored to see if lower BTK occupancies will still equate to clinical efficacy. For this reason, clinical response alone, and not BTK occupancies, is recommended to guide dose adjustment in **Part B**.

Given the efficacy seen in this pemphigus study to date at varied clinical severities, and the updated, supporting, chronic, GLP toxicology ([Section 1.3](#)), there is clinical equipoise to study PRN1008 monotherapy (or with low dose CS) in patients with mild-to-severe (baseline PDAI 8-60), corticosteroid-naïve or relapsing PV, with close observation and appropriate corticosteroid rescue protocols.

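### The Part A tolerability definition omits 'or greater' for non-gastrointestinal events, so read literally a related Grade 3–4 liver event counts as well tolerated

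*Protocol*

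**What the plan says.** Protocol Section 4.6 governs dose adjustment. In Part A the dose depends on clinical response, trough BTK occupancy and tolerability. A dose is well tolerated when there is "absence of Grade 3 or greater gastrointestinal AEs, or Grade 2 non-gastrointestinal AEs, including liver function changes, related to PRN1008 therapy". The same definition is repeated in the footnote to Table 2, in Part A SAP Section 3.4, and in the footnote to the table in Part A SAP Appendix 15.2.

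Table 2 covers the first 4 weeks of Part A and is headed as general guidelines. For responders who tolerate the drug poorly, the action begins "Reduce to 300 mg" (bid). For a suboptimal response with trough occupancy below 50% and good tolerability, it is "Follow rescue criteria if triggered, if not, increase dose to 600 mg bid".

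Between the definition and the table, Section 4.6 asks investigators to use risk-benefit judgement and adds: "In general, PRN1008 should be stopped and conventional therapy started when tolerability is poor and clinical response is also suboptimal". The two Table 2 cells for that combination, once rescue has been ruled out, read "if not maintain dose at 400 mg bid if feasible" (occupancy at or above 50%) and "increase dose to 600 mg bid if tolerability allows" (below 50%).

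**The concern.** The definition decides which half of Table 2 applies to a patient. The words 'or greater' qualify the gastrointestinal limb only. Protocol Section 12.4 treats Grades 1 to 5 as distinct categories, so a Grade 3 event is not a Grade 2 event. The definition therefore catches a moderate liver event and misses a severe one.

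The liver is a foreseeable place for this to matter. Section 1.3.1 reports that in dogs dosed above 30 mg/kg "changes in liver function (mainly ALT and AST), loss of appetite, and associated weight loss were observed", and calls these observations clinically significant. Section 1.4.1 describes one healthy volunteer in Study PRN1008-006 with a reversible Grade 2 rise in ALT. At stake is a patient-safety instruction about keeping, raising or lowering the dose, not an inferential quantity.

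**Working it through.** The plan states no figure here to reproduce. The check applies the definition to each grade, follows the result through Table 2, and looks for a rule elsewhere that would correct it.

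**Step 1. Apply the definition.** Take a patient whose related events are all of the kind shown.

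| Related event | As written | With 'or greater' added |
|---|---|---|
| Gastrointestinal, Grade 1–2 | well tolerated | well tolerated |
| Gastrointestinal, Grade 3 or higher | not | not |
| Non-gastrointestinal, Grade 1 | well tolerated | well tolerated |
| Non-gastrointestinal, Grade 2 | not | not |
| Non-gastrointestinal, Grade 3–4 | **well tolerated** | **not** |

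Only the last line changes. A patient who also has a related non-gastrointestinal event recorded at Grade 2 already fails the definition.

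**Step 2. Follow it through Table 2.** The table has 2 response levels × 2 occupancy levels × 2 tolerability levels = 8 rows, 4 for each tolerability class. In the suboptimal rows the rescue criteria come first; the action shown applies if they are not triggered.

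| Response | Trough occupancy | Well-tolerated row | Poorly tolerated row |
|---|---|---|---|
| Responder | ≥ 50% | maintain 400 mg bid | reduce to 300 mg bid |
| Responder | < 50% | maintain 400 mg bid | reduce to 300 mg bid |
| Suboptimal | ≥ 50% | maintain 400 mg bid | maintain, conditional on feasibility |
| Suboptimal | < 50% | increase to 600 mg bid | increase, conditional on tolerability |

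The literal reading moves the Grade 3–4 patient from the right-hand action column to the left: 3 rows maintain and 1 increases. In the 2 responder rows it removes a dose reduction. In the 2 suboptimal rows it removes the condition attached to the action. It also takes the patient outside the general stop advice, which applies only when tolerability is poor.

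**Step 3. Look for a correction elsewhere.**
- Protocol Appendix 1A: the rescue triggers are a potentially life-threatening flare, PDAI of 45 or more, and no disease control by 4 weeks. All concern disease activity, not tolerability.
- Protocol Section 16.4: withdrawal for adverse events is at the investigator's discretion, with no grade or liver threshold.
- Protocol Section 12.7: abnormal laboratory results that lead to a change in study drug are recorded, but the section does not say when to make the change.
- Protocol Section 12.1: the safety committee meets about every 3 months at first, which is slow for a decision in the first 4 weeks.
- Part A SAP Section 9.2 and Part B SAP Section 5.5.2: the liver-injury displays are reporting rules.

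None supplies a grade-based or liver-specific dosing rule.

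**Step 4. Gauge the exposure.** Protocol Section 2.3 reports that, at 18 January 2018, none of the 21 treated patients had discontinued or dose-reduced because of a treatment-related event. On occupancy, Section 2.1 gives "20/21) had adequate BTK occupancies (mean 86% pre dose at steady-state": 20/21 = 95.2%, leaving 1/21 = 4.8%. If 'adequate' there means at least the 50% trough cut-off of Table 2, which Section 2.1 does not say, about 1 of 21 patients was in the below-50% rows at all, before response and tolerability are considered.

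**The case against.** The strongest reply is that this is a drafting slip nobody would follow. The sentence sets a stricter threshold for non-gastrointestinal events than for gastrointestinal ones. A literal reading reverses that by accepting a Grade 3 liver event and rejecting a Grade 3 gastrointestinal one. The next sentence calls for risk-benefit judgement, and the table is labelled as guidance. Chemistry is drawn at Days 15 and 29 within the relevant window. Part B dosing does not use the term: Table 3 bars escalation where tolerability issues preclude it. No SAP analysis classifies patients by tolerability, since the Part A SAP groups them by maximum dose. The Part B SAP introduction records that the last Part A patient completed on 20 June 2019, so the table has little prospective use.

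All of that stands as to consequence. It shows that misapplication is unlikely; it does not make the stated threshold correct. Good sense has to override the definition, and that sense is needed most for the more severe events.

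A reader might also infer that Table 2 contradicts the stop advice and forces a poorly tolerating, poorly responding patient to continue or escalate. The documents do not support that. The advice stands directly above the table in the same section, both cells are conditional, and Section 16.4 lets the investigator withdraw a patient for adverse events. Making a stop the default in the below-50% cell would be a dosing choice on which reasonable people could differ.

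**Conclusion.** The point holds as a wording error in a decision threshold, and it should be fixed. It concerns one definition in four copies, and its effect on dosing is confined to Table 2: Part A, first 4 weeks. Read literally, it places a related Grade 3–4 non-gastrointestinal event in rows that maintain the dose (3 of 4) or raise it (1 of 4), and displaces the dose reduction in the 2 responder rows.

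This rests on a literal reading. The intended meaning is almost certainly Grade 2 or greater, and few if any patients are likely to have been affected. It would go too far to infer that the protocol requires dosing through severe liver toxicity, or that patients were in fact misdosed; nothing in the documents shows either. No endpoint, sample size or error rate is touched. The relation between the Table 2 cells and the stop advice is an editorial matter only.

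**What to change.** Change the non-gastrointestinal limb to 'Grade 2 or greater non-gastrointestinal AEs' in the Section 4.6 text, the Table 2 footnote, Part A SAP Section 3.4 and the footnote in Part A SAP Appendix 15.2. Carry the corrected wording into any later protocol that reuses the definition.

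Optionally, add to the two suboptimal, poorly tolerated cells of Table 2, and to their copies in SAP Appendix 15.2, a cross-reference to the general stop advice in the Section 4.6 text. The actions in those cells need not change.

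The cost is two words in four places and one routine protocol amendment. Under Protocol Section 14.4 that means submission to the review board, and to regulators if required, with approval before use. No extra patients, visits or procedures are needed.

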5 PROTOCOL DEVIATIONS

The Principal Investigator is responsible for complying with all protocol requirements, and applicable global and local laws regarding protocol deviations. Principia does not allow intentional or prospective deviations from the protocol unless necessary to eliminate an immediate hazard to study subjects. The Principal Investigator is responsible for immediately (within 24 hours) notifying Principia of a major protocol deviation to permit Principia to determine the impact of the deviation on the subject and/or the study:

Primary Principia Contact:

Secondary Principia Contact:

The Principal Investigator is responsible for notifying Independent Ethics Committee (IEC)/Independent Review Board (IRB) regulatory authorities, and contract research organization (CRO) Clinical Monitors of all protocol deviations.

6 STUDY POPULATION

The study population is male or female patients with newly diagnosed (i.e., naïve to an effective induction treatment regimen) or relapsing, biopsy-proven, mild to severe PV (PDAI 8-60), for whom an initial period of PRN1008 monotherapy is judged clinically acceptable.

Because patients without mucosal involvement but with a medical history suggestive of PV are allowed into the study, some patients with clinical features suggestive of the pemphigus foliaceus (PF) variant of the disease may be enrolled.

6.1 Inclusion Criteria (Part A and Part B unless noted below)

1. Male or female patients, aged 18 to 80 years old, with biopsy-proven (positive direct immunofluorescence and appearance on H&E microscopy), mild-moderate PV in **Part A** (PDAI 8 to 45) and mild-severe PV in **Part B** (PDAI 8 to 60)
2. Newly diagnosed or relapsing patients for whom an initial period of PRN1008 monotherapy or combination therapy with low-dose corticosteroids (≤ 0.5 mg/kg of prednis[ol]one or equivalent), is judged clinically acceptable, provided tapering of the corticosteroid treatment regimen is anticipated with good clinical response to PRN1008
3. BMI > 17.5 and < 40 kg/m² **Part A only**
4. Adequate hematologic, hepatic, and renal function (absolute neutrophil count $\geq 1.5 \times 10^9/L$, Hgb > 9 g/dL, platelet count $\geq 100 \times 10^9/L$, AST/ALT $\leq 1.5 \times$ ULN, albumin ≥ 3 g/dL, creatinine \leq ULN (**Part A**) and creatinine $\leq 1.5 \times$ ULN (**Part B**))
5. Female patients who are of reproductive potential must agree for the duration of active treatment in the study to use an effective means of contraception (hormonal contraception methods that inhibits ovulation, intrauterine device, intrauterine hormone-releasing system, bilateral tubal ligation, vasectomized partner, condoms or sexual abstinence). Unless surgically sterile, postmenopausal females should have menopause confirmed by FSH testing.
6. Able to provide written informed consent and agreeable to the schedule of assessments.

6.2 Exclusion Criteria

1. Previous use of a BTK inhibitor

*Patients enrolled in a previous version of this protocol who are still in their 12-week active treatment period with PRN1008 are eligible to continue treatment, initially with their current dose level, under this amended protocol for an additional 12 weeks, i.e. 24 weeks total, following review and signature of the EC approved patient's consent. Patients who completed **Part A** and did not discontinue the study due to a medical condition that might compromise safety assessments or for a PRN1008 related adverse event may be screened for entry under **Part B**.*

2. Pregnant or lactating women

3. ECG findings of QTc > 450 msec (males) or > 470 msec (females), poorly controlled atrial fibrillation (i.e. symptomatic patients or a ventricular rate above 100 beats/min on ECG), or other clinically significant abnormalities
4. A history of malignancy of any type, other than surgically excised non-melanoma skin cancers or in situ cervical cancer within 5 years before the day of dosing
5. Use of immunologic response modifiers with the following periods prior to Day 1: as concomitant therapy, other immunologic response modifiers not detailed in this exclusion apart from corticosteroids; *1 week*: cyclophosphamide; *4 weeks*: IVIG, Kinaret (anakinra) and Enbrel (etanercept); *12 weeks*: Remicade (infliximab), Humira (adalimumab), Simponi (golimumab), Orenzia (abatacept), Actemra (tocilizumab), Cimzia (certolizumab), Cosentyx (secukinumab), plasmapheresis; *6 months*: Rituxan/MabThera (rituximab), ofatumumab, any other anti-CD20 antibody, other long-acting biologics
6. More than 0.5 mg/kg of prednis(ol)one per day (“low dose corticosteroids”) within the two weeks prior to Day 1
7. Use of proton pump inhibitor drugs such as omeprazole and esomeprazole (it is acceptable to change patient to H2 receptor blocking drugs prior to the first dose of PRN1008)
8. Concomitant use of known strong-to-moderate inducers or inhibitors of CYP3A ([Appendix 2](#)) within 3 days or 5 half-lives (whichever is longer) of study drug dosing
9. Use of CYP3A-sensitive substrate drugs ([Appendix 3](#)) with a narrow therapeutic index within 3 days or 5 half-lives (whichever is longer) of study drug dosing including, but not limited to, alfentanil, astemizole, cisapride, cyclosporine, dihydroergotamine, ergotamine, fentanyl, pimozide, quinidine, sirolimus, tacrolimus, or terfenadine
10. Has received any investigational drug (or is currently using an investigational device) within the 30 days before receiving the first dose of study medication, or at least 5 times the respective elimination half-life time (whichever is longer)
11. History of drug abuse within the previous 12 months
12. Alcoholism or excessive alcohol use, defined as regular consumption of more than approximately 3 standard drinks per day
13. Refractory nausea and vomiting, malabsorption, external biliary shunt, or significant bowel resection that would preclude adequate study drug absorption
14. History of anorexia nervosa or periods of three months or more of low body weight (BMI < 17.5) in the past 5 years
15. Donation of a unit or more of blood or blood products within 4 weeks prior to Day 1
16. History of solid organ transplant
17. History of epilepsy or other forms of seizure in the last 5 years
18. Positive for screening for HIV, hepatitis B (surface and core antibodies unrelated to vaccination), or hepatitis C (anti-HCV antibody confirmed with Hep C RNA)

19. Positive interferon-gamma release assay (IGRA) (e.g., T-spot TB Test, QuantiFERON®-TB Gold, or QuantiFERON®-TB Gold Plus (QFT Plus) at Screening. Unless, the patient has latent TB and all of the following 3 conditions are true:
- a. Chest X-ray does not show evidence suggestive of active tuberculosis (TB) disease
 - b. There are no clinical signs and symptoms of pulmonary and/or extra-pulmonary TB disease
 - c. Documented receipt of one of the following prophylactic treatment regimens:
 - i. Oral daily Isoniazid for 6 months
or
 - ii. Oral daily Rifampin (RIF) for 4 months
or
 - iii. Isoniazid and Rifapentine weekly for 3 months (3HP)

On a case by case basis, after discussion and approval by the Sponsor, a local TB test that is negative and is considered equivalent to 1 of the above tests may be used for eligibility. For example, if a QuantiFERON®-TB Gold, or QuantiFERON-TB Gold Plus (QFT Plus) is positive and a local blood test or T-Spot TB test is negative, the patient may be enrolled using the local result upon approval of the Sponsor.

20. History of serious infections requiring intravenous therapy with the potential for recurrence
21. Live vaccine within 28 days prior to baseline or plan to receive one during the study
22. Any other clinically significant disease, condition, or medical history that, in the opinion of the Investigator, would interfere with subject safety, study evaluations, and/or study procedures

6.3 Prior and Concomitant Therapy

6.3.1 Prior Therapy

Not Permitted:

Use of immunologic response modifiers within the following periods prior to Day 1:

- One week for cyclophosphamide
- Four weeks for Kinaret® (anakinra), intravenous gamma globulin (IVIG), and Enbrel® (etanercept)
- 12 weeks for Remicade® (infliximab), Humira® (adalimumab), Simponi® (golimumab), Orencia® (abatacept), Actemra® (tocilizumab), Cimzia® (certolizumab), Cosentyx™ (secukinumab), plasmapheresis

- 6 months for Rituxan®/MabThera® (rituximab), ofatumumab, any other anti-CD20 antibody, or any other long-acting biologic

